5.6.7. Vital Signs

Vital sign measurements, including blood pressure (systolic and diastolic, while participant is seated), pulse rate, respiratory rate and temperature will be listed for the Safety Population.

5.6.8. Pregnancy Test Analyses

Urine pregnancy test is taken at screening, prior to every treatment (initial, touch-up, and maintenance), and study exit. Participants with a positive result for the Safety Population throughout the study period will be presented as a listing.

5.7. Other Analyses

5.7.1. Subgroup analyses

Analysis of the primary effectiveness endpoint, ALJDS responder status at Month 6, will be performed on the mITT population during the CP for the following subgroups:

- ! Investigational sites by treatment group.
- ! Total volume injected (total injection volume at initial and touch-up treatments combined): \leq median and $>$ median. This analysis will be done for treatment group only.
- ! Route of injection (ie, needle or cannula). The primary effectiveness endpoint at Month 6 will be presented by route of injection (i.e., needle or cannula). A participant is defined to be in the needle group if only needle is used at both initial and touch-up treatments. A participant is defined to be in the cannula group if either only cannula is used or cannula in combination with needle at either initial or touch-up treatments. A homogeneity test will be done to compare the primary effectiveness endpoint at Month 6 between the needle and cannula groups at alpha = 0.15. This analysis will be done only for the treatment group.

! Baseline ALJDS score. If the baseline ALJDS score is different for the left and right jaws then the worse score is used as baseline score.

No multiplicity adjustment will be performed.

5.7.2. Impact of COVID-19

All COVID-19 related data collected on the eCRFs will be presented in listings.

5.8. Interim Analyses

No interim analysis is planned for this study.

6. Supporting Documentation

6.1. Appendix 1: List of Abbreviations

AE	adverse event
AESI	adverse events of special interest
ALJDS	Allergan Loss of Jawline Definition Scale
CI	confidence interval
COVID-19	coronavirus disease 2019
CP	control period
eCRF	electronic case report form
EI	Evaluating Investigator
GAIS	Global Aesthetic Improvement Scale
ISR	injection site response
MedDRA	medical dictionary for regulatory activities
mITT	modified intent-to-treat
MP	maintenance treatment period
PT	preferred term
SAE	serious adverse event
SAP	statistical analysis plan
SOC	system organ class
TEAE	treatment-emergent adverse event
TESAE	treatment-emergent serious adverse event
TI	Treating Investigator
TP	treated period
VMT	VOLUX maintenance treatment population
VT	VOLUX treated population
WHO	World Health Organization

6.2. Appendix 2: List of Changes

6.2.1. Changes to Protocol-Planned Analyses

The following changes to the analyses specified in the statistical sections of Study V25L-002 Amendment 2 (Approved version dated 11-March-2019) have been implemented in this SAP:

1. Four analysis populations [mITT, Safety, Observed Primary Endpoint, VT and VMT] are defined instead of the 2 analysis populations (ITT and Safety) stated in the protocol [Section 4. Populations for Analysis].
2. The primary effectiveness endpoint will be analyzed using the mITT population instead of the ITT population as stated in the protocol [Section 5.3 Primary Effectiveness Endpoint Analysis].
3. Multiple imputation will be used as the primary method for the analysis of the primary endpoint instead of using the last observation carried forward. More specifically, multiple imputation with 30 imputed datasets will be applied to participants with missing Month 6 ALJDS values, generated using the following model (performed by treatment group) [Section 5.3 Primary Effectiveness Endpoint Analysis]:

$$\text{Month 6 ALJDS} = \beta_0 + \beta_1 \text{Baseline ALJDS} + \beta_2 \text{Month 1 ALJDS} + \beta_3 \text{Month 3 ALJDS}$$

4. The analysis of the effectiveness and/or safety variables will be summarized by the VT and VMT populations in TP and MP, respectively. In CP, the analysis of the effectiveness and/or safety variables will be summarized by the mITT and Safety populations [Section 5.3.4 Supplementary Analyses and 5.6.3 Adverse Events].
5. Baseline for the primary effectiveness endpoint is defined as the last non-missing value on or before the latter of randomization date or first treatment date in the control period [Section 5.1 General Considerations]. In the protocol, Baseline is defined as the last assessment by EI prior to randomization.

6.2.2. SAP Version History

The following are the changes to version 2 of SAP:

1. Updated the criteria for receiving touch-up treatment based on the protocol in Section 1.2.
2. Updated the number of imputed datasets used for the primary effectiveness endpoint analysis from 5 to 30 datasets in Sections 2 and 5.3.2 to reduce variability and increase efficiency of estimates. Changed the seed in Step 1 to keep it consistent with what was used in the lines of SAS code. Added the “likelihood=augment” option in the PROC MI SAS code in case the data has either complete separation pattern or quasi-complete separation pattern.
3. The naming of the analysis population for the sensitivity analysis of primary endpoint, ALJDS responder status at Month 6 was changed from “Completer Population” to “Observed Primary Endpoint” in Sections 4, 5.3.3, and 6.2.1. The definition of this population refers to the completion of the primary timepoint visit (ie., Month 6 of CP). This naming change is aimed to avoid potential confusion with study completion.
4. Updated the definition of TP for the control group to “follow-up period once the participants receive the optional treatment” and starts in the end date of CP in Section 5.1.
5. The definition of “baseline” for the effectiveness and safety variables in Sections 5.1 and 6.2.1 was changed to “the last non-missing assessment prior to the latter of randomization or first treatment in the control period” due to possibility of participants who were mistreated (ie., either randomized to VOLUX but was not treated or randomized to Control but received VOLUX).
6. Specified that 95% CI for continuous variables will be based on the standard normal distribution in Section 5.1.
7. Added that the exact binomial method will be used to compute 95% CI for categorical variables in Section 5.1.
8. Added a bullet regarding how if any data is collected after exit then it will be summarized in the tables and listings in Section 5.1.
9. The wording of “Rasch transformed score” were specified for the analyses of FACE-Q Satisfaction with Lower Face and Jawline and FACE-Q Appraisal Lines: Marionette in Sections 5.4.1, 5.4.2, and 5.5 and to enhance clarity and consistency with Appendix 6.5.
10. The definition of change from baseline was moved from Section 5.4.1 to Section 5.1

11. Added clarification in Section 5.4.2 that analyses will be performed on the mITT population.
12. The imputation for the missing items of FACE-Q Satisfaction with Lower Face and Jawline and FACE-Q Appraisal Lines: Marionette were added to Section 5.4.2 and 5.5, respectively.
13. Added the definition of baseline for the control group for FACE-Q Satisfaction with Lower Face and Jawline in Section 5.5 since this assessment is not done on the control group during the control period.
14. Added clarification on the subset of participants on whom the analyses of FACE-Q Appraisal Lines: Marionette will be performed in Section 5.5. Additionally, the definition of responder on FACE-Q Appraisal Lines: Marionette was added to this section.
15. The wording of “responder status” was added to the “number (%) of responder” analysis for the endpoints of ALJDS, GAIS (EI and participant), FACE-Q Satisfaction with Lower Face and Jawline, and FACE-Q Appraisal Lines: Marionette in Table 5-6 for clarity.
16. The analysis of ISR in Section 5.6.4 was revised to include: (1) ISR summary by maximum duration instead of simply by duration and (2) analysis of “other symptoms” based on the coded terms assigned by the Medical Safety Physician.
17. Added clarification regarding analysis for 2-point discrimination and pronunciation video as well as definition of baseline in the control group during TP for Jaw Functional Limitation Scale in Section 5.6.6.
18. Subgroup analysis of the primary effectiveness endpoint by baseline ALJDS was added in Section 5.7.1.
19. A data listing to tabulate the COVID-19 related data collected during the study is added to Section 5.7.2.
20. Since no interim analysis regarding the primary and secondary endpoints was performed the text regarding the same was deleted in Section 5.8.
21. A summary for baseline ALJDS at jaw level as well as subject level was added in Section 6.3.2.
22. Changed the population for medical history listing from mITT population to all randomized participants in Section 6.3.4.

CONFIDENTIAL

JUVÉDERM VOLUX™ XC

Statistical Analysis Plan V25L-002

23. Removed the summary of prior and concomitant medications and changed the population for prior and concomitant medications listing from mITT population to all randomized participants in Section 6.3.5.
24. Added details regarding analysis windows for safety assessments in Section 6.4.1.2.

6.3. Appendix 3: Supporting Study Information

6.3.1. Demographics

Demographic parameters (age [years]; sex; race; ethnicity) will be summarized descriptively in total and by treatment group for the mITT populations. Age (years) will be calculated relative to informed consent date.

6.3.2. Baseline and Disease Characteristics

Baseline characteristics will be summarized in total and by treatment group for the mITT population as follows:

- ! Weight (kg), height (cm), and body mass index (kg/m²)
- ! Sun exposure (hours per day)
- ! Fitzpatrick Skin Phototype (Each phototype, and by phototype groups, ie, I and II, III and IV, V and VI)
- ! Smoking history (status, amount, tobacco product, frequency, and duration in months)
- ! Baseline ALJDS score at jaw level as well as subject level. For the subject level summary, if the right and the left jaws have different ALJDS score then the worse score is will be used for the summary

6.3.3. Protocol Deviations

Significant protocol deviations will be identified. Unique participants reporting significant protocol deviations will be summarized in total and by treatment group for all randomized participants as described in [Table 6-1](#).

Listing of significant protocol deviations will be provided.

Table 6-1 **Protocol Deviation Summary**

Endpoint	Description	Timing	Methodology
Significant protocol deviations	Number (%) of participants with significant protocol deviation will be summarized (All randomized)	During study period	Categorical descriptive statistics

6.3.4. Medical History

Abnormalities in participants' medical, surgical, cosmetic and dental history, encompassing abnormalities, surgeries, and procedures reported as occurring before the Screening Visit, will be coded using MedDRA, version 22.1 or newer. Listing will be provided for all randomized participants.

6.3.5. Prior/Concomitant Medications

Medications will be coded using the WHO Drug Dictionary, version March 2017 or newer. Listing of prior and concomitant medications will be provided for all randomized participants.

Table 6-2 Prior and Concomitant Medications

Endpoint	Description	Timing	Methodology
Prior medications	Medications taken before the study treatment for the treatment group or before randomization for the control group	Screening	Listing
Concomitant medications	Medications taken during the corresponding period	CP, TP, MP	Listing

6.4. Data Handling Convention

6.4.1. Analysis Window

6.4.1.1. Effectiveness

All scheduled and unscheduled visits with complete dates will be assigned visit windows and used for analysis (Table 6-3, Table 6-4, Table 6-5, and Table 6-6). However, if a scheduled visit with incomplete date is available with no other visits with complete date during the visit window, then the visit with incomplete date may be used for analysis, and the nominal visit will be used as the visit window (eg, if the only assessment collected for Month 3 visit window is on a Month 3 eCRF with incomplete date, then those data will be used for the Month 3 assessments).

For the treatment group, the effectiveness day is calculated relative to the last treatment date (either the initial treatment if no touch-up is performed, or the touch-up treatment, or the maintenance treatment date). If the analysis date is on or after the last treatment date, then the effectiveness day = analysis date - the last treatment date + 1. If the analysis date is before the last treatment date, then the effectiveness day = analysis date - the last treatment date.

For the control group during the no-treatment control period, the effectiveness day is calculated relative to the randomization date. If the analysis date is on or after the randomization date, then

effectiveness day = analysis date - randomization date + 1. If the analysis date is before the randomization date, then effectiveness day = analysis date - randomization date.

For the control group after receiving optional treatment, the effectiveness day is calculated relative to the last treatment date (either the initial treatment, if no touch-up is performed, or the touch-up treatment). If the analysis is on or after the last treatment date, then effectiveness day = analysis date - last treatment date + 1.

If there are multiple visits occurring within a single visit window with relevant data, the visit closest to the target day will be used in the analysis of the corresponding visit windows. If 2 visits are equal distance to the target day and are the same type of visit, then the later visit will be used.

Analysis visit windows for effectiveness endpoints are defined as follows:

If analysis date \geq reference date, then

$$\text{Analysis day} = \text{analysis date} - \text{reference date} + 1$$

If analysis date $<$ reference date, then

$$\text{Analysis day} = \text{analysis date} - \text{reference date}$$

Table 6-3 Effectiveness Analysis Visit Definitions for Treatment Group during the Treated Period

Scheduled Visit for Effectiveness Measure	Target Day of the Visit	Analysis Visit Window
Screening ^a	N/A	Screening visit; No more than 30 days prior to randomization
Baseline	N/A	Randomization/Initial Treatment visit
Touch-up Treatment ^b	Day 31 Post Initial Treatment	Day of the Touch-up Treatment
Last Treatment ^c	Day 1 Post Last Treatment	Day 1
Month 1	Day 31 Post Last Treatment	Day 2 to Day 61
Month 3	Day 91 Post Last Treatment	Day 62 to Day 136
Month 6	Day 181 Post Last Treatment	Day 137 to Day 226
Month 9	Day 271 Post Last Treatment	Day 227 to Day 316
Month 12	Day 361 Post Last Treatment	Day 317 to Day of Maintenance Treatment ^d or Day of Study Exit, whichever is earlier

^a Participants may have screening and randomization on the same day. In such cases, only randomization visit is relevant.

^b Not all participants will receive touch-up treatment.

^c If touch-up is not performed then reference date is the date of initial treatment, otherwise reference date is the date of touch-up treatment.

^d Not all participants will receive maintenance treatment.

Table 6-4 Effectiveness Analysis Visit Definitions for Control Group during the Control Period

Scheduled Visit for Effectiveness Measure	Target Day of the Visit	Analysis Visit Window with Touch-up
Randomization Day ^a	Day 1	N/A
Month 1	Day 31	Day 2 to Day 61
Month 3	Day 91	Day 62 to Day 136
Month 6	Day 181	Day 137 to Day of Optional Treatment or Day of Study Exit, whichever is earlier

^a Participants may have screening and randomization on the same day. In such cases, only randomization visit is relevant. Randomization date is the reference date.

Table 6-5 Effectiveness Analysis Visit Definitions for Control Group during the Treated Period

Scheduled Visit for Effectiveness Measure	Target Day of the Visit	Analysis Visit Window
Optional Treatment	N/A	Initial Treatment visit
Touch-up Treatment ^a	Day 31 Post Initial Treatment	Day of the Touch-up Treatment
Last Treatment ^b	Day 1 Post Last Treatment	Day 1
Month 1	Day 31 Post Last Treatment	Day 2 to Day 61
Month 3	Day 91 Post Last Treatment	Day 62 to Day 136
Month 6	Day 181 Post Last Treatment	≥ Day 137

^a Not all participants will receive touch-up treatment.

^b If touch-up is not performed then reference date is the date of initial treatment, otherwise reference date is the date of touch-up treatment.

Table 6-6 Effectiveness Analysis Visit Definitions for Treatment Group during the Maintenance Period

Scheduled Visit for Effectiveness Measure	Target Day of the Visit	Analysis Visit Window
Maintenance Treatment ^a	Day 1 Maintenance Treatment	Day of Maintenance Treatment
Month 1 after Maintenance Treatment	Day 31 Post Maintenance Treatment	Day 2 to 61 Post Maintenance Treatment
Month 3 after Maintenance Treatment	Day 91 Post Maintenance Treatment	≥ Day 62 post Maintenance Treatment

^a Not all participants will receive maintenance treatment. Date of maintenance treatment is the reference date.

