Subjects who discontinue early, ie, before the Month 6 Visit, are to complete applicable study visit procedures and Early Exit Visit procedures.

For female subjects of childbearing potential, must be confirmed negative before randomization.

Table 5 Schedule of Visits and Procedures: Control Group (Delayed-Treatment Period)

1 able 5	Schedule (	)1 V 15115 a	anu 110	ccuui es.	Contro	n Grou	p (Delay	cu-11ca	tillent i	CII	ju)	
Study Period	Day 1 Opt ITx a	Day 3 After Opt ITx	Day 14 After Opt ITx	Day 30/ Opt TTx b	Day 3 After Opt TTx	Day 14 After Opt TTx	Month 1	Month 3	Month 6	Month 9	Month 12/ Study Exit	Early Exit Visit c
Visit Window	Month 6 Visit +14 Days	-1/+2 Days	±3 Days	-2/+10 Days	-1/+2 Days	±3 Days	-2/+10 Days	±10 Days	±10 Days		±10 Days	
Urine pregnancy test d	X			X					X			X
Snellen visual acuity (TI or designee)	X e		X	X e		X						
Confrontational visual fields (TI or designee)	X e		X	X e		X						
Ocular motility (TI or designee)	X e		X	X e		X						
Pretreatment anesthesia	X			X								
Treatment injections (TI)	X			X								
Procedural pain (subject)	X			X								
Jaw Functional Limitation Scale (subject)	$X^{f}$		X	$X^{f}$		X	X	X	X			
FACE-Q Satisfaction with Lower Face and Jawline (subject)	$X^{\mathrm{f}}$						X	X	X			
3D facial digital imaging	X			$X^f$			X	X	X			
Pronunciation video recording	$X^{f}$			$X^{f}$			X	X	X			
GAIS (subject)							X	X	X			
ALJDS (EI) g							X	X	X			
Facial sensation assessment (EI)	$X^{f}$			$X^f$			X	X	X			
GAIS (EI)							X	X	X			
Weight									X			
Safety telephone call		X			X						X	
Subject safety e-diary h	Continuous Continuous											
Concomitant medications, procedures, therapies	Continuous Monitoring						X					
Adverse Events	Continuous Monitoring								X			

Approval Date: 11-Mar-2019

- EI = Evaluating Investigator; GAIS = Global Aesthetic Improvement Scale; ITx = initial treatment; Opt = optional; TI = Treating Investigator; TTx = touch-up treatment
- a Optional initial treatment can occur same day or within 14 days after the Month 6 Visit. If optional initial treatment occurs on the same day as the Month 6 Visit, duplicate assessments do not have to be repeated.

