3. Sample Size Determination

Sample size is determined to provide adequate power to demonstrate that the product is effective as well as safe. A sample size of 120 participants in the treatment group and 40 participants in the control group will provide > 99% power to detect a difference of at least 40% in the responder rates between the 2 groups. This calculation is based on a 1-sided Fisher's exact test at the 2.5% level. The treatment group is assumed to have at least an 80% responder rate and the control group is assumed to have at most a 40% responder rate. Assuming a screen fail rate of 25% and a drop-out rate of 15% between randomization and the Month 6 visit, up to 280 participants will be enrolled, with at least 144 participants and at most 162 participants randomized to the treatment group and at least 48 participants and at most 54 participants randomized to the control group (3:1 ratio).

This sample size is considered adequate to determine the safety profile of the product in the jawline area. Assuming a screen fail rate of 25%, a 5% drop-out rate between randomization and initial treatment for the treatment group, and a 15% drop-out rate between randomization and optional treatment for the control group, it is estimated that at least 176 subjects will be treated in the study. With 176 treated subjects, there is at least 92% power to detect an AE related to treatment with an incidence rate of 1.5% in the population using a 1-sided exact binomial test at the 2.5% level.

The commercial software, PASS (2008, Version 8.0.13), was used for the power calculation. The sample size calculation used an inequality test for 2 proportions to demonstrate that the treatment group is superior to the control group. The safety calculation used an inequality test for 1 proportion.

4. Populations for Analysis

The 5 analysis populations will consist of participants as defined in [Table 4-1](#).

Table 4-1 Analysis Populations

Population	Definition	Study Treatment Assignment
mITT	All randomized participants with non-missing baseline on the ALJDS scale on both sides of the jaw	As randomized
Observed Primary Endpoint	All mITT participants who have Month 6 assessment on the ALJDS scale on both sides of the jaw	As randomized
Safety	All randomized participants who receive study treatment (VOLUX or control)	As treated ^a

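### A Month 6 rating on Day 227 or later counts as observed for controls but is reassigned and its Month 6 value imputed for VOLUX

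*SAP*

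**What the plan says.** SAP Section 6.4.1.1 sets the rule for effectiveness data: "All scheduled and unscheduled visits with complete dates will be assigned visit windows and used for analysis". The nominal visit label is a fallback for a scheduled visit with an incomplete date when no fully dated visit lies in the window. Where several visits share a window, "the visit closest to the target day will be used in the analysis of the corresponding visit windows".

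Both arms have a Month 6 target of Day 181 and a window that opens on Day 137. Days are counted from last treatment for VOLUX and from randomization for controls. The windows close differently:

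- VOLUX (Table 6-3): Month 6 is "Day 137 to Day 226" and Month 9 is "Day 227 to Day 316". Month 12 starts on Day 317.
- Control, control period (Table 6-4): Month 6 is "Day 137 to Day of Optional Treatment or Day of Study Exit, whichever is earlier".

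Footnote a of Protocol Table 5 dates optional treatment from the visit itself: "Optional initial treatment can occur same day or within 14 days after the Month 6 Visit".

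On missing values, SAP Section 6.2.1 says that "multiple imputation with 30 imputed datasets will be applied to participants with missing Month 6 ALJDS values". The predictors are baseline, Month 1 and Month 3 ALJDS, and imputation is done within treatment group (Section 5.3.2). Sensitivity analysis 1 uses the Observed Primary Endpoint population, defined in Table 4-1 as "All mITT participants who have Month 6 assessment on the ALJDS scale on both sides of the jaw".

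**The concern.** The second primary hypothesis compares Month 6 responder rates between randomized arms. A rule that decides whether a rating is a Month 6 observation should not depend on the arm. Here it does for any fully dated Month 6 visit held on Day 227 or later: the rating is used directly in one arm and replaced by a model-based value in the other.

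The limit on the control window gives no protection. Optional treatment is scheduled from the actual Month 6 visit, so a late visit pushes the limit back with it. Study exit likewise cannot come before a visit that the participant attends. Delayed visits were foreseeable, since SAP version 2 (April 2020) added COVID-19 listings (Section 5.7.2).

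**Working it through.** **1. The plan's own figure.** Inputs from SAP Section 3: 120 versus 40 evaluable, 80% versus 40% responders, 1-sided Fisher's exact test at 2.5%. Exact enumeration over both binomial distributions gives power 0.9941, which agrees with the stated figure of more than 99%. The 15% drop-out allowance also works: 144 × 0.85 = 122.4 and 48 × 0.85 = 40.8. No sample-size figure needs correcting.

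**2. The two tables applied to the same day.** Assume a full visit date and no other rating in Days 137 to 226.

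| Day of the Month 6 visit | VOLUX (Table 6-3) | Control (Table 6-4) |
|---|---|---|
| 181 | Month 6, observed | Month 6, observed |
| 226 | Month 6, observed | Month 6, observed |
| 227 to 316 | Month 9; Month 6 missing, imputed | Month 6, observed |
| 317 onward | Month 12; Month 6 missing, imputed | Month 6, observed |

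The reassigned VOLUX rating is not a predictor in the imputation model. It stays in the by-visit summaries as Month 9 unless another visit lies closer to Day 271. The late control rating is used as an endpoint and also helps to fit the control arm's imputation model.

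**3. How late a visit must be.** 226 − 181 = 45, so only visits more than 45 days past target are affected. The protocol allows ±10 days at Month 6 in both arms (Tables 3 and 4), about Day 171 to Day 191. The VOLUX cut-off lies 226 − 191 = 35 days beyond that.

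**4. Sensitivity analyses (Table 5-3).** Analysis 1 needs a windowed Month 6 value, so it excludes the late VOLUX participant and keeps the late control. Analysis 2 repeats multiple imputation after excluding participants for EI unblinding or an ineligible baseline grade. Neither changes the windows.

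**5. Possible size.** The documents give no late-visit rate, so everything in this step is an assumption. The direct shift in an arm's rate is

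shift = (late share) × (late-rating response − imputed response),

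and the second factor may have either sign.

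- Control arm, which the Table 6-4 cap would change. One late rating of 48 is 1/48 = 2.1%, so its direct effect is at most 2.1 points. With a gap of 30 points either way it is 2.1% × 30 = 0.6 points. Two late ratings with the same gap give 4.2% × 30 = 1.3 points.
- VOLUX arm, which only a nominal-visit run would change. With 5% late and a 20-point gap, 1.0 point; with 10% and 30 points, 3.0 points; with 20% and 30 points, 6.0 points.

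**6. Power.** Suppose 2%, 5%, 10% or 20% of about 122 evaluable VOLUX participants lose Month 6 to the cut-off and are simply dropped. Exact Fisher power against 40 controls is then 0.994, 0.994, 0.993 or 0.992. Power for the 50% criterion stays above 0.999.

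**The case against.** The strongest defence is that the difference follows a consistent convention. Bounded windows are cut midway between scheduled targets: (181 + 271)/2 = 226. The last visit of each period has no numeric upper day, as with Month 12 in Table 6-3, Month 6 in Table 6-5 and Month 3 in Table 6-6. Controls have no Month 9 visit in the control period, so there is no midpoint to cut at. This explains how the cell arose. It does not justify different treatment of the same late rating in the primary randomized comparison.

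A second defence is that a rating on Day 227 or later lies nearer to Month 9 than to Month 6, so declining to call it Month 6 is reasonable. That stands, and it is a reason to apply the same limit to controls.

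Three stronger readings are tempting, and the documents do not support them:

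- **That the rule favours VOLUX, or inflates its rate by a stated amount.** This takes the late rating as the true Month 6 response. If the effect wanes, a rating at least 46 days past target would understate Month 6 response. On the control side, a late rating could be higher or lower than the value imputed in its place. No direction follows.
- **That both primary hypotheses are affected.** The 50% test uses VOLUX data alone, and the VOLUX window is the same whatever Table 6-4 says.
- **That late VOLUX ratings are thrown away.** They are lost to the Month 6 endpoint but reassigned to Month 9 or Month 12. They drop out of the by-visit summaries only if another visit is closer to that target.

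**Conclusion.** The point holds as a low-impact inconsistency in the between-group comparison. For a fully dated Month 6 visit on Day 227 or later, with no other rating in Days 137 to 226, the arm decides whether the Month 6 value is observed or imputed. The Observed Primary Endpoint analysis has the same asymmetry, with exclusion in place of imputation.

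The effect is zero if no visit runs more than 45 days past target. Otherwise its size depends on late shares and response gaps that the documents do not give, and its sign is undetermined. Under the assumptions shown, one or two late controls move the control rate by about a point or less, and the planned power is barely changed. The conclusions are unlikely to turn on it. The case for acting is that the rule should be the same in both arms and that the change is small.

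**What to change.** In SAP Table 6-4, define the control Month 6 window as running from Day 137 to the earliest of Day 226, the day of optional treatment and the day of study exit. The same late limit then applies in both arms. Add one sensitivity run of the primary endpoint that uses the nominal Month 6 visit in both arms, whatever its day. The two parts do different jobs: the cap makes the rule equal but leaves every VOLUX classification as it is, while the nominal-visit run shows what the cut-off does in both arms.

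The cost is one table cell and one extra run. The downside is that a few late control ratings, in the smaller arm (48 to 54 randomized), may be imputed in the primary analysis; the nominal-visit run keeps them. One consequence needs checking. For controls who do not take optional treatment, Table 5-1 ends the Control Period at Day 181 when Month 6 is missing. A control whose only rating from Day 137 on falls after Day 226 would therefore get that end date, as already happens for VOLUX.
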